## **8.5. Assigning Patients to Treatment Groups**

See [Section 9.3.](#)

## **8.6. Prior and Concomitant Medications**

Prior treatments for WM will be recorded in the eCRF as well as treatments for any significant illness in the past year.

Any concomitant medication used from time of Screening through last study visit will be recorded in the eCRF, including dose, dosage regimen, and indication (reason for its prescription).

### ***8.6.1. Prohibited Treatments***

The exclusion criteria specify treatments prohibited at the time of study entry ([Section 1.5.3](#)).

While patients are receiving study treatment, other treatments for WM are prohibited. Patients who discontinue treatment prematurely and have completed the EOT visit, may receive available or investigational treatment for their disease at any time based on the judgment of their physician. If such treatment is initiated prior to the EOS visit (scheduled for 30 days after last dose of study drug), this will be recorded in concomitant medications and considered in assessment of any new AEs.

### ***8.6.2. Other restrictions***

None.

## **8.7. Treatment Compliance**

All doses of study drug will be administered by study personnel. Injections of study drug may be administered in one of two contexts:

- ***Study site*** – defined as the site designated by the participating Investigator. On Study Days when a Physical Examination is scheduled (that is, at Day 1 and at the first weekly doses of Weeks 2 and 5 of Cycle 1 and at Weeks 1 and 5 of additional cycles), it is expected that study drug will be administered at the study site.
- ***Non-study site administration by a visiting nurse*** – With the agreement of the patient and the Investigator, doses not administered at the study site may be administered by a visiting nurse who has been trained in the protocol and approved by the Sponsor.
  - The Sponsor will arrange for a Central Pharmacy to prepare and dispense the patient's study treatment, which will be packaged as required and shipped by overnight delivery service. To protect the integrity of the treatment, the shipping container must be held unopened in a cool, dry, protected place.
  - The visiting nurse will open the container, inspect the materials, confirm they are correct, and proceed with pre-dose procedures, study drug administration, and post-dose procedures.

- The used syringe and packaging materials will be disposed of per policy of the Central Pharmacy.
- The visiting nurse will maintain appropriate source documents; the events will be entered into the electronic data capture (EDC) system and copies of the source documents provided to the site.

## **8.8. Accountability of Investigational Drug Supplies**

Study drug will be provided by the Sponsor. The Investigator at each study site is responsible for the control of the study drug, and will identify trained and experienced personnel to handle it in accordance with the protocol and appropriate GCP and GMP principles (Central Pharmacy will be responsible for study drug stored at Central Pharmacy and dispensed to the patient). This includes:

- Storing the drug in a secure, controlled-access location.
- Storing the drug under the specified conditions, including daily monitoring and recording of storage temperature.
- Maintaining records of the receipt of study drug and providing acknowledgement of receipt.
- Dispensing and administering study drug only in accordance with the protocol.
- Maintaining drug accountability records indicating the disposition of study drug, including a Drug Dispensing Log containing the following information:
  - Identification of the patient to whom the study drug was dispensed.
  - Date(s) and quantity of the study drug dispensed to the patient.
- Having all records and drug supplies available for inspection by the study monitor.

### ***8.8.1. Disposition of Study Drug***

At any time during or after completion of the study, the site must obtain written authorization from the Sponsor regarding the final disposition of any remaining study drug; that disposition must be appropriately documented. Typical procedures for handling any remaining study drug include the following:

- Returning study drug to the Sponsor.
- Destroying study drug at the study site according to the site's institutional standard operating procedure.

## 9. STUDY EVENTS AND EVALUATIONS

### 9.1. Schedule of Events

The schedule for all study events is detailed in [Table-4](#). [Table-5](#) gives an estimate of blood volumes required.

The schedule is presented relative to the day and time of dosing. All Days are relative to the calendar day of the first injection of study drug, designated Day 1. All weeks are relative to Week 1 of each cycle, defined as Day 1 through Day 7, inclusive. All times are relative to injection, designated 0 hour; “pre-dose” vital signs are to occur within 1 hour prior to injection; all other pre-dose procedures are to occur prior to injection on the same calendar day.

### 9.2. Screening Procedure

The screening evaluation may be performed up to 21 days prior to dosing. Written informed consent will be obtained before any study-specific procedures are performed. The consent procedure must be recorded in source documentation. All patients who sign an informed consent form (ICF) will be entered into the EDC system within 48 hours of consent. To minimize patient risk and discomfort, the radiologic imaging and bone marrow biopsy scheduled at Screening will be performed only *after* the patient meets all other inclusion and exclusion criteria.

Waldenström’s macroglobulinemia is a rare disease and patients often travel considerable time and distance to be managed at tertiary referral centers. To facilitate rapid completion of screening and enrollment and thereby avoid the need for multiple trips, Investigators may, with the approval of the Sponsor, perform screening laboratory studies at their local laboratory, including safety labs (see [Section 9.7](#)), cryoglobulins and cold agglutinins, and qualifying total serum IgM and monoclonal serum IgM protein levels (see [Section 9.4.2](#)). In such cases, central laboratory tests scheduled at Screening will be handled as follows:

- Concurrent safety labs (see [Section 9.7](#)) will not be submitted to the central lab.
- Blood and urine samples will be submitted to the central lab for the tests relating to monoclonal protein (see [Section 9.4.2](#)) and to Investigational studies (see [Section 9.9](#)) to support longitudinal data analysis.

Pre-dose on Day 1, safety labs will be sent to the central laboratory for *all patients* as scheduled and used as the baseline (pre-treatment) safety laboratory values to support longitudinal analysis.

### **9.3. Enrollment Procedure**

The following procedure is to assure that patients enrolled across multiple sites are assigned to the appropriate cohort and receive the appropriate dose level. Patients who have completed all screening procedures and are assessed as eligible by the Investigator will be reviewed with the Sponsor or the Sponsor's designated representative. After acceptance, the Investigator and site pharmacy will be provided the following information in writing (by email and/or fax):

- The patient's assigned unique study number, to be marked on all study-specific documents.
- The patient's assigned dose level.

### **9.4. Assessments of Waldenström's Macroglobulinemia**

Laboratory assessments for disease status (see [Section 9.4.2](#)) will be conducted at Screening, every 4 weeks  $\pm$  1 week (Week 1 and Week 5 of each cycle), every 12 weeks  $\pm$  4 weeks during the Follow-up Phase, at the EOT visit, and at the EOS visit.

Clinical assessments for disease status (see [Section 9.4.1](#)) will be conducted at Screening, every 8 weeks  $\pm$  1 week (Week 1 of every cycle), every 12 weeks  $\pm$  4 weeks during the Follow-up Phase, at the EOT visit, and at the EOS visit.

Radiologic imaging will be performed at Screening and at EOT visit or as clinically indicated.

Bone marrow biopsy and aspirate will be performed at Screening, EOT, and to document complete response as appropriate (see [Section 16.2](#)).

A medical history specific to WM will be collected at Screening and will include, but is not limited to: a detailed review of the patient's malignancy, prior treatments, relevant current or past abnormalities or diseases, and signs and symptoms of WM at baseline ([Section 9.6.1](#)).

#### **9.4.1. Clinical Assessments**

- ECOG performance status.
- Clinical assessment for tumor status including assessment of lymphadenopathy, hepatomegaly and splenomegaly.

#### **9.4.2. Laboratory Assessments Relating to Total IgM and Monoclonal Protein**

The following laboratory assessments will be performed by a central laboratory approved by the Sponsor. As noted above, patients being enrolled on the basis of local lab data may be qualified based on local results for serum IgM monoclonal protein levels, but at the time of Screening they will still have blood and urine samples submitted so that the panel below may be performed at the central lab.

- Total serum IgM by nephelometry (i.e., total IgM or IgM).
- Quantification of serum IgM monoclonal and total protein by densitometry, i.e., Serum Protein Electrophoresis with immunofixation (i.e., monoclonal IgM or M-spike).
- Serum Free Light Chains (sFLC) and ratio.

- Serum  $\beta$ 2-microglobulin.
- Serum viscosity.
- Urine Free Light Chains (uFLC) and ratio.

#### **9.4.3. Radiologic Imaging**

Computed tomography or magnetic resonance imaging scan of chest, abdomen and pelvis to assess for lymphadenopathy and organomegaly. Modality of the scan must be consistent throughout the study. Interim scans may be performed at the request of the Investigator and with the approval of the Idera Medical Monitor based on new signs or symptoms.

#### **9.4.4. Bone marrow biopsy and aspirate**

The procedures for collecting, processing, and transporting bone marrow biopsy and aspirate specimens will be detailed in the Bone Marrow Biopsy manual. Bone marrow biopsy and aspirate specimens will be sent to the central pathologist for confirmation of disease status, flow cytometry, and to the central laboratory for investigational studies of tumor cells (see [Section 9.9](#)). The percent lymphoplasmacytic cell involvement will be noted for each biopsy performed. Bone marrow biopsy and aspirate will be performed at Screening, EOT, and to document complete response as appropriate (see [Section 16.2](#)).

### **9.5. Evaluation of Response to Treatment and Disease Status**

The criteria for response to treatment are provided in [Section 16.2](#) (based on the full text of the VIth International Workshop classification [1]). Central laboratory serum total IgM and serum monoclonal IgM values are to be used to evaluate response to treatment (refer to [Section 9.4.2](#)).

The Third International Workshop for WM also defined the following categories [26]:

**Not evaluable response:** Reserved for situations in which there is insufficient data for a determination of response to treatment.

**Delayed response:** A delayed response is described particularly after treatment with purine analogue or monoclonal antibody. The recommendation was that patients should be followed for at least 12 weeks after treatment initiation to be considered unresponsive to therapy.

### **9.6. General Clinical Assessments**

#### **9.6.1. Medical History, including WM**

At the Screening visit, the Investigator will obtain a comprehensive medical history to ensure eligibility of the patients, including the following items:

- A detailed review of the course of the patient's malignancy, including clinically significant complications such as systemic infections, bleeding events, etc.
- Prior treatments, including supportive therapy (agent, duration, best clinical response, AEs related to treatment, and reason for discontinuation).
- Relevant current or past abnormalities or diseases (including surgical procedures) of the following systems: allergic (including drug sensitivity), cardiovascular,

dermatologic, endocrine/metabolic, gastrointestinal, gynecologic, hematologic/lymphatic, hepatic/biliary, immunologic, infectious, musculoskeletal, neurologic/psychiatric, renal, and respiratory.

- A separate eCRF will be provided to record signs and symptoms of WM at Baseline, including but not limited to: bleeding events, fatigue, anemia, thrombocytopenia, leukemia/neutropenia, fever, hyperviscosity, neuropathy, lymphadenopathy, weight loss, headache, night sweats, and vision changes.

Past history should include all significant illnesses that the patient has experienced and have resolved within the 12 months prior to signing informed consent. Illnesses active at the time of informed consent will be regarded as concomitant illnesses. Concomitant illnesses that worsen or illnesses with onset after obtaining informed consent will be recorded on the AE form in the EDC (see [Section 10](#)), with particular attention to whether the onset was before or after administration of the first dose of study drug. If a WM sign or symptom recorded at Screening worsens, it will be captured as an AE.

#### ***9.6.2. Physical Examination and Body Weight***

Complete physical examinations will include examination of general appearance, skin, neck (including thyroid), eyes, nose, throat, heart, lungs, abdomen, lymph nodes, extremities, reproductive (in event of recent history, symptoms or AEs related to reproductive system) and nervous system and measurement of body weight. Exam of reproductive system when needed may be performed by the Investigator or delegated to a specialist.

Height and weight will be evaluated at Screening and the body mass index will be calculated.

Any clinically significant changes in physical exam identified after obtaining informed consent will be recorded using the AE form in the EDC (see [Section 10](#)).

#### ***9.6.3. Vital Signs***

Vital signs include heart rate (HR), blood pressure (BP), respiratory rate, and temperature. Where feasible, vital signs should be measured before blood is drawn and after the patient has been sitting comfortably for 5 minutes with the BP cuff in place on the non-dominant arm. Blood pressure and HR measurements will be taken first and may be done manually or by automated recorder. Respiratory rate will be determined by observation for at least 30 seconds. Temperature will be obtained using an electronic (rapid reading) device.

Vital sign measurements will be assessed by the Investigator as either ‘normal,’ ‘abnormal, not clinically significant,’ or ‘abnormal, clinically significant.’ Clinically significant abnormal vital sign measurements will be reported as an AE, and, if possible, should be repeated at clinically relevant intervals until resolved or stabilized.

#### ***9.6.4. Electrocardiogram***

Standard 12-lead ECG will be obtained after the patient has been semi-recumbent for ~10 minutes. The following ECG parameters will be recorded: ventricular rate, RR interval, PR interval, QRS interval, QT interval, QTc interval, and QTc method. Electrocardiograms are to be performed at Screening, at pre-dose and 2 hours post-dose on Day 1 of Cycle 1, and pre-dose at

the first dosing visit of Weeks 1 and 5 of each cycle thereafter. In addition, an ECG is to be performed at 2 hours post-dose on Day 1 of each odd-numbered cycle.

#### **9.6.5. *Injection Site Reaction (ISR) Assessments***

Injection site reactions will be documented in detail for each individual injection as described in [Table-11](#). Each ISR shall also be captured on the AE form in the eCRF.

The Investigator will assess the injection site as scheduled and perform the following:

- Pain, tenderness, pruritus and induration: grade using the scale provided;
- For induration, also record the actual maximal linear diameter as a continuous variable;
- Erythema, record the actual maximal linear diameter as a continuous variable;
- Blisters, ulceration, necrosis: indicate presence or absence and record the maximal linear diameter, if applicable.

**Table-11. IMO-8400 Subcutaneous Injection Site Grading (Local Reactions)**

Finding	Mild	Moderate	Severe
Pain	Present; no limitations in ADL	Limitations in age-appropriate instrumental ADL or requires repeated non-narcotic pain reliever	Limitations in self-care ADL or interferes with sleep, or requires repeated narcotic pain reliever
Tenderness	Mild discomfort with pressure	Discomfort with touch	Discomfort elicited by clothing or bedsheets
Pruritus (itch)	Present, but minimally distracting	Present, distracting during routine activities	Interferes with sleep
Induration (swelling, edema)	Present; no limitations in ADL	Limitations in age-appropriate instrumental ADL or requires repeated treatment (excluding systemic steroids).	Limitations in self-care ADL or requires treatment with systemic steroids

Pain: discomfort or unpleasant feeling (e.g., headache) experienced while at rest or with activity; in addition to location, the patient's description may include intensity as well a distinctive quality (e.g., burning, stabbing).

Tenderness: discomfort elicited when the area is touched either intentionally or accidentally.

Pruritus (itch): an unpleasant sensation that evokes the desire or reflex to scratch. (In contrast, pain and tenderness evoke a reflex to withdraw.)

Activities of daily living (ADL) are classified into two subsets:

- instrumental ADL, e.g., preparing meals, shopping for groceries or clothes, using the telephone, managing money;
- self-care ADL, e.g., bathing, dressing and undressing, feeding self, using the toilet, taking medications, and not being bedridden.

When reporting injection site reactions as an AE, the Investigator should report in the verbatim term the words "injection site reaction," along with the specific reaction symptom (such as erythema), and select the severity grade based on the National Cancer Institute-Common Terminology Criteria for Adverse Events (NCI-CTCAE) guidelines which are presented in [Table-12](#).

**Table-12. Intensity of AE of Injection Site Reactiona**

Mild	Moderate	Severe	Life-threatening
Tenderness with or without associated symptoms (e.g., warmth, erythema, itching)	Pain; lipodystrophy; edema; phlebitis	Ulceration or necrosis; severe tissue damage; operative intervention indicated	Life-threatening consequences; urgent intervention indicated

a. Based on NCI-CTCAE v.4.03. Definition of Injection Site Reaction: A disorder characterized by an intense adverse reaction (usually immunologic) developing at the site of an injection.

## 9.7. Safety Laboratory Studies

The laboratory tests indicated below will be performed by a central laboratory designated by the Sponsor (except for sites approved to use local laboratory results for screening as detailed in [Section 9.2](#)). The procedures for collecting, processing, and transporting the required blood samples will be detailed in the laboratory manual.

The Investigator may order additional local laboratory tests consistent with their routine standard of care.

### 9.7.1. Safety Laboratory Tests

#### Hematology Panel

*Hemoglobin	Mean corpuscular hemoglobin (MCH)	*WBC differential (absolute cell counts):
*Hematocrit	Mean corpuscular hemoglobin concentration (MCHC)	- Neutrophils
*Red blood cell count (RBC)	Mean corpuscular volume (MCV)	- Lymphocytes
*White blood cell (WBC) count		- Monocytes
*Platelet count		- Eosinophils
		- Basophils

#### Clinical Chemistry Panel

*Glucose	Magnesium	*Alanine aminotransferase (ALT)
*Urea	Calcium	*Aspartate aminotransferase (AST)
*Creatinine	Phosphate	*Alkaline phosphatase (AP)
*Sodium	Uric Acid	*Total bilirubin
*Potassium	Cholesterol	Total protein
*Chloride	Triglycerides	Albumin
*Bicarbonate	Low density lipoprotein (LDL)	Lactate dehydrogenase (LDH)
C-reactive protein (CRP)	High density lipoprotein (HDL)	Creatine phosphokinase (CK)

\* Laboratory tests comprising focused panel to be performed on Weeks 3 and 7 of each cycle.

### **Serum Complement Testing**

Complement component 3 (C3)  
Complement component 4 (C4)  
50% hemolytic complement (CH50)

### **Coagulation Panel**

Prothrombin Time (PT)	International normalized ratio (INR)
Activated partial thromboplastin time (aPTT)	Fibrinogen

### **Urinalysis**

Specific gravity, pH, ketones, glucose, protein, blood (commercial dipstick may be used); microscopic examination, including quantitation of white blood cells and red blood cells.

### **Serologic tests (Screening only)**

Hepatitis B surface antigen (HBsAg)	Antibody to human immunodeficiency virus (HIV)-1 and HIV-2	Antibody to hepatitis C virus (HCV)
-------------------------------------	--	-------------------------------------

### **Pregnancy tests (Females only)**

beta-human chorionic gonadotropin ( $\beta$ -hCG)

### **9.7.2. Reporting of Safety Laboratory Tests**

Results of safety laboratory tests are expected to be available to the Investigator within 48 hours. Procedures for the Investigator assessment of the results are detailed in [Section 10.2](#). Procedures for the analysis of laboratory data are described in [Section 10.4.5](#).

### **9.7.3. Repeating Abnormal Laboratory Tests**

Laboratory tests showing abnormal or exclusionary values at Screening may be repeated no more than once. After dosing, abnormal laboratory tests assessed as “clinically significant” values may be repeated as often as deemed clinically necessary by the Investigator until the test values are clinically acceptable or until an explanation other than drug effect is given.

## **9.8. Pharmacokinetic Assessments**

Blood samples for plasma levels of IMO-8400 will be collected as scheduled. Samples will be analyzed for IMO-8400 concentration using a validated bioanalytical method (estimated sensitivity, 20 ng/mL). Pharmacokinetic data will be analyzed on an individual basis.

For each cohort, the plasma IMO-8400 concentration data will be analyzed by non-compartmental PK analysis. The following parameters will be determined as appropriate: observed maximum plasma concentration ( $C_{max}$ ), time of  $C_{max}$  ( $T_{max}$ ), and AUC from 0 to last measurable plasma concentration ( $AUC_{0-t}$ ). Pharmacokinetic parameters will be compared across IMO-8400 dose levels. Descriptive statistics will be provided for all PK parameter values by dose and time, as appropriate.

## **9.9. Investigational Laboratory Studies**

The following laboratory studies relate to assessing the pharmacologic effects of the investigational agent. Samples will be collected as scheduled and sent to the Central Lab, where they will then be sent to Sponsor-designated qualified labs for testing. The clinical significance

of these tests is unknown at this time and therefore the results will not be assessed by the Investigator.

Tumor cells from the bone marrow biopsy samples will be assayed for:

- Presence of MyD88 L265P mutation, and, if indicated, other somatic mutations in genes encoding proteins in the TLR and BCR signaling pathways (e.g., CARD11, IRAK4, BTK). Samples will be retained for up to 1 year after completion of the study to support possible future development of a companion diagnostic assay.

Serum samples will be assayed for:

- Levels of cytokines IL-6, IL-12, IL-17, IP-10; additional or alternative cytokines may be assessed using the samples collected.
- Antibodies to IMO-8400.
- NF-κB pathway inhibition.

## 10. SAFETY ASSESSMENTS (ADVERSE EVENTS)

### 10.1. Definition of Adverse Events

#### 10.1.1. *Adverse Event*

An AE is any untoward medical occurrence temporally associated with the use of a medical product in a patient, ***whether or not*** the event is considered causally related to the medical product. An AE can be a new occurrence or an existing process that increases significantly in intensity or frequency.

An AE in a clinical trial may be ***any*** of the following:

- Unfavorable and unintended *symptom reported by the patient* — patients will be encouraged to report TEAEs spontaneously; general, non-directed questioning may also be used to elicit reports of AEs;
- Clinical *sign detected by the Investigator* — observations by other study personnel will be reported to the Investigator for evaluation;
- Abnormal result from a *laboratory study* or other *diagnostic procedure* that meets at least one of the following criteria:
  - Results in termination of study drug;
  - Leads to treatment;
  - Leads to further diagnostic tests (other than a single repeat for confirmation);
  - Is assessed as “clinically significant” by the Investigator (see [Section 10.2](#)).

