### **8.4.1. Pre-Treatment Criteria**

IMO-8400 should not be administered until the following conditions are met:

- Hemoglobin  $\geq 7.5$  g/dL
- ANC  $\geq 1,000/\mu\text{L}$
- Platelets  $\geq 50,000/\mu\text{L}$
- All other laboratory abnormalities to baseline or grade  $\leq 1$

These parameters will be measured at local laboratories at Week 1 and Week 5 of each cycle.

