### **8.4.2. Variances in Dose Administration Schedule**

**Once weekly dosing:** for patients assigned to dose levels of 0.6, 1.2, 2.4, or 3.6 mg/kg/week. The expectation is that patients will be dosed each week on the same day of the week. To allow for holidays and other scheduling issues, individual doses may be administered up to 2 calendar days earlier or later than expected, while remaining on the same schedule. Doses should not be administered fewer than 5 calendar days after the preceding dose.

If, for any reason (e.g., scheduling or toxicity), dosing is interrupted more than 2 calendar days beyond expected, then the next dose should be administered as soon as feasible and the schedule reset to once weekly on the next convenient weekday.

**Twice weekly dosing:** for patients assigned to the dose level of 1.2 mg/kg twice weekly (2.4 mg/kg/week). The total weekly exposure will be administered as a 2 separate SC injections of 1.2 mg/kg per injection, respectively, over the course of the week. The expectation is that patients will be dosed twice each week on the same day of the week, with (approximately) 72 or 96 hours (3 or 4 calendar days, respectively) between injections. The minimum interval between successive doses may not be less than 48 hours (2 calendar days). If, for any reason (e.g., scheduling or toxicity), the interval between successive doses is 6 or more calendar days, then the next dose should be administered as soon as feasible and the twice weekly dosing schedule resumed.

**Extended dosing interruptions.** If, for any reason, dosing is interrupted for more than 21 calendar days due to toxicity, the patient should be discontinued from study treatment unless

the Investigator and the Idera Medical Monitor agree that it is in the patient's best interest to continue.

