#### **10.2. *Investigator Assessment of Safety Laboratory Tests***

The Investigator will review the results of all Safety Laboratory tests (see [Section 9.7.2](#)) and designate any results outside of the reference range as **either** of the following:

- Abnormal, not clinically significant (NCS).
- Abnormal, clinically significant (CS).

In making this judgment, the Investigator will consider all available information, including the patient's clinical condition, all available laboratory results (central and local), and the potential for false positive test results. In addition, laboratory studies that result in the actions specified in [Section 10.1.1](#) will be classified as CS.

Any result assessed as CS will be recorded as an AE *unless* it is consistent with one or more of the following:

- Process noted in the medical history.
- Ongoing AE already recorded.
- Expected course of the primary disease under study.

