#### **10.4.6. Management of Study Drug upon Occurrence of an Adverse Event**

For each AE the Investigator will indicate which one of the following actions regarding the administration of study drug was taken because of that AE:

- **Discontinued (withdrawn)** — study drug was stopped permanently due to the AE.
- **Dosing Interrupted** — study drug regimen was modified by being temporarily halted, i.e., 1 or more doses were not administered, but drug was not stopped permanently.
- **Dose Decreased** — study drug regimen was modified by subtraction, i.e., by decreasing the frequency, strength or amount.
- **None** — no change in the administration of study mediation.

For patients whose treatment is paused and then resumed at a lower dose level as detailed in [Section 6.5.2](#), the management of study drug will be recorded as “Dose Decreased.”

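### A laboratory result that only holds or delays dosing becomes an AE solely on the Investigator's clinical-significance label, so some holds can be missing from the TEAE summaries

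*Protocol*

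**What the plan says.** Protocol Section 10.1.1 gives four ways in which an abnormal laboratory result becomes an AE. Three are automatic: the result "Results in termination of study drug"; it "Leads to treatment"; or it "Leads to further diagnostic tests (other than a single repeat for confirmation"). The fourth is the Investigator's judgment that the result is clinically significant.

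Section 10.2 ties judgment to action: "laboratory studies that result in the actions specified in" Section 10.1.1 must be classed as CS. For every other out-of-range value the Investigator chooses CS or NCS. A CS label is not the last step either: "Any result assessed as CS will be recorded as an AE *unless* it is consistent with one or more of the following", and the exemptions are medical history, an AE already recorded, and the expected course of the disease. Section 10.4.5 reports laboratory results as AEs when they are CS.

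Section 8.4.1 sets the pre-treatment rule: "IMO-8400 should not be administered until the following conditions are met". The conditions are hemoglobin of at least 7.5 g/dL, ANC of at least 1,000/µL, platelets of at least 50,000/µL, and other laboratory abnormalities at baseline or grade 1 or lower.

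Section 10.4.6 asks, for each AE, which of the listed "actions regarding the administration of study drug was taken because of that AE". Its interruption category is worded in terms of doses not given. For once-weekly dosing, Section 8.4.2 resets the schedule when "dosing is interrupted more than 2 calendar days beyond expected". For twice-weekly dosing its trigger is an interval of 6 or more calendar days between doses.

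Sections 10.3 and 12.3 build the TEAE summaries from recorded AEs with onset after the first dose.

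**The concern.** The primary objective is safety and tolerability by dose level. A laboratory value that stops a dose under the protocol's own rule is relevant to tolerability. Section 10.4.6 accepts this by treating interruption and reduction as consequences worth recording, but Section 10.1.1 leaves both off the list that creates the AE to which they would be attached. Whether such a hold is counted can therefore depend on how a site uses the CS label.

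This cannot be left to the analysis plan. An analysis plan can derive late doses from dosing dates, but it cannot restore an AE, a causality assessment or an action code that was never collected. The rule has to be settled in the protocol and the eCRF.

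**Working it through.** The question is mainly textual, so each laboratory-driven hold in the protocol is traced through the recording rules.

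| Hold | Automatic AE route? | Why |
|---|---|---|
| Complement drop (6.5.4) | Yes | The required work-up goes beyond one repeat (it includes an ECG), so the further-tests criterion is met |
| Platelets below 25 x 10^9/L (6.5.5) | Yes | An anti-platelet antibody test is required |
| Laboratory DLT (6.3.1, 6.5.2) | Yes | A potential DLT is defined as a treatment-emergent AE |
| Worsening of a WM sign recorded at Screening (9.6.1) | Yes | Captured as an AE without reference to the CS label; the baseline form names anemia, thrombocytopenia and neutropenia |
| Any other hold under 8.4.1 | No | 8.4.1 requires neither treatment nor an added test; only the CS judgment remains |

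The CS exemptions in 10.2 apply to the first two rows as well.

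The last row is not empty:
- **Platelets from 25 to below 50 x 10^9/L.** These block dosing under 8.4.1, but the antibody test in 6.5.5 is not called for.
- **ANC below 1,000/µL.** This blocks dosing, but 6.3.1 counts neutropenia as a DLT only if it is grade 4 for more than 7 days, or grade 3 or 4 with sustained fever.
- **Another abnormality above both baseline and grade 1.** This blocks dosing and can lie well below the DLT grade.

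If such a value clears at the first repeat and is labelled NCS, the chain is: no criterion in 10.1.1 is met; 10.2 does not force CS; no AE is recorded; 10.4.6 has nothing to attach an interruption to; and the TEAE summaries in 12.3 do not include it. The value is still graded, listed and shown in the shift tables, but those tables show grade and not that a dose was held.

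Dose reduction adds little to the gap in practice. Section 6.5.2 provides for it after a laboratory DLT or dose modifying event. The gap is mainly one of holds and delays.

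**Size.** Let h be the share of patients with a hold of this residual kind and c the share of those labelled CS and recorded. The recorded rate is h x c. The protocol gives neither h nor c, so the loss, h x (1 - c), cannot be computed.

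The one stated figure that relies on AE capture is in Section 12.1: 22 patients give a 90% probability of seeing an AE of 10% incidence. It reproduces: 1 - (1 - 0.10)^22 = 0.9015. For a laboratory event of 10% incidence that leads only to such a hold, the probability of at least one recorded AE becomes 1 - (1 - 0.10c)^22, with c **assumed**:
- c = 0.90: 1 - 0.910^22 = 0.874
- c = 0.75: 1 - 0.925^22 = 0.820
- c = 0.50: 1 - 0.950^22 = 0.676
- c = 0.25: 1 - 0.975^22 = 0.427

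This shows how far the stated figure leans on the label for this one class of event. It is not an estimate of what will happen.

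**The case against.** A rule that makes laboratory AEs depend on clinical significance is a defensible choice, and most holds are already caught by the routes in the table. Cytopenia is a recognised complication of WM, so the Screening rule in 9.6.1 may cover many of the hemoglobin, ANC and platelet cases. An abnormality that lasts beyond one recheck arguably meets the further-tests criterion. Laboratory tests are a safety endpoint in their own right in 12.3, and late doses can be found from dosing dates. All of this stands, and it narrows the gap to a transient hold that was not a recorded baseline sign and was judged NCS. It does not close the gap, because none of these routes records that hold as a toxicity with a dosing consequence.

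A reader might infer three stronger things that the protocol does not support.

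- **That laboratory-driven holds as a class are lost.** The table shows otherwise.
- **That the dose relation is flattened.** If c is the same at two dose levels, the recorded rates are c x h1 and c x h2. Their ratio is unchanged and only the absolute difference shrinks. Nothing in the protocol suggests that labelling differs by dose, and 12.3 plans no formal comparison.
- **That 10.4.6 and 8.4.2 flatly contradict each other.** One codes AE actions and the other governs scheduling, and a temporary halt can be read to include a late dose. What remains is an ambiguity: it is unclear whether a dose given late because of an AE is coded as an interruption.

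**Conclusion.** The point holds in a limited form. Section 10.1.1 names termination but not interruption, delay or reduction, and 10.2 inherits the omission. As a result, a hold under 8.4.1 that falls outside the other capture routes is recorded as an AE only at the Investigator's discretion. When it is labelled NCS, both the AE and its action entry are absent; the abnormal value is not.

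The size is unknown. It depends on how often such holds occur and how often they are labelled CS, and the protocol states neither. The conclusion rests on reading 10.1.1 as the complete list of automatic triggers, and on the protocol describing no other field that links a laboratory hold to its cause (the eCRF is not shown). The point concerns recording only. No view is taken on the thresholds or on when dosing should be held.

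**What to change.** 1. In 10.1.1, change the first laboratory criterion to: *Results in interruption, delay, reduction or termination of study drug*. Section 10.2 then classes such results as CS without further edits. Its exemptions for medical history, an ongoing AE and expected disease course would still apply, so capture improves but is not absolute.
2. Reconcile the interruption category in 10.4.6 with 8.4.2 separately for each schedule, so that a dose delayed because of an AE is coded in one way. A single 2-day limit will not serve, because 8.4.2 uses it for once-weekly dosing only; the definition should refer to the 8.4.2 rule for the patient's schedule.

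The cost is a few words in two sections and matching eCRF guidance. The downside is somewhat more laboratory AEs, including some low-grade ones, because an isolated chemistry value above grade 1 that delays a dose would now be classed as CS. No dosing rule or threshold changes.
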